11.6 Sensitivity analyses

Intervention adherence

A Complier Average Causal Effect (CACE) analysis to assess the impact of compliance on treatment estimates will be undertaken for the primary outcome (DASH score at 4-months). Compliance will be based on whether the participant received allocated treatment and also using surgeon self-report forms and image analysis of intra-operative images for fidelity. A two-stage IV regression approach will be used with mixed-effects regression to reflect the primary analysis. This model will be fit using the ivregress stata command. The primary analysis model will be repeated but the variable for randomised treatment group will be replaced with the variable for compliance. The option vce (cluster) will be used to account for repeated measures.

Missing data

We anticipate that missing data for the statistical analysis will be relatively small. The primary outcome will be collected at the 4-months clinic visit which is a routine visit. In the event participants cannot attend in person, procedures are in place to collect the data remotely.

The amount of missing data will be mitigated by including all data in the primary analysis model, which allows the inclusion of any patient with complete baseline data and valid outcome data at one or more follow-up points.

The amount of missing data will be reported for each randomised arm, and we will also compare the baseline characteristics of participants who are included in the primary analysis to ensure that any attrition has not produced any imbalance in the groups in important covariates. To account for any possible bias, a logistic regression will be run to predict non-response (no questionnaires received post-randomisation) including variables collected prior to randomisation. The primary analysis will then be repeated including as covariates all variables found to be significantly predictive of non-response to determine if this affects the parameter estimates.

The primary analysis and the above model including variables associated with outcome and missingness will assume missing outcome data are missing at random (MAR). However, it is possible that participants who failed to complete follow-up questionnaires differed from those who completed follow-up questionnaires (e.g. had poorer recovery and therefore would have scored lower on the DASH if they had completed the follow-up). This would mean the data were missing not at random (MNAR), and would represent a departure from the MAR assumption.

The sensitivity of the primary analysis results to departures from the MAR assumption may be explored using a pattern-mixture model, implemented using the rctmiss Stata command (13, 14) This command currently supports the use of fixed-effect models only, and therefore a linear regression model comparing the primary outcome at 4-months post-randomisation will be used, adjusting for treatment group, age at randomisation, prescribed NSAIDs, previous elbow fractures, diabetes status, smoking status, and drinks alcohol.

The pattern mixture model works by including a sensitivity parameter quantifying the departure from the MAR assumption. For example, if we expected that those who failed to complete the follow-up at 4-months post-randomisation on average would have scored two points lower on the DASH than those who did attend the follow-up, the sensitivity parameter would be equal to 2. The pattern-mixture model can then be used to obtain an estimate of the treatment effect given this level of departure from the MAR assumption. The rctmiss command estimates the treatment effect for varying values of the sensitivity parameter ranging from zero up to any positive value, which allows for the assessment of the impact of varying degrees of departure from the MAR assumption on the treatment effect estimate.

The rctmiss command will be used to produce a graph of the adjusted mean difference in DASH score between treatment groups for varying values of the sensitivity parameter. This will be done assuming the value of the sensitivity parameter is equal in both groups (missing data are equally informative in both groups), and also assuming the sensitivity parameter is equal to zero in the control group and varying in the intervention group, and vice versa (missing data are only informative in one group and not the other).

While the results of this sensitivity analysis will not be directly comparable to the primary analysis model, it will be able to give an indication of how sensitive the estimate of the treatment effect is to departures from the MAR assumption in the primary outcome data.

In addition to the above analysis, patterns of missingness amongst participants will be summarised descriptively.

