11.5 Primary analysis

DASH scores will be analysed using a mixed-effects regression model, with DASH scores at 4, 12 and 18-months follow-up as the dependent variable, adjusting for baseline DASH scores (pre-injury), age at randomisation (continuous), prescribed NSAIDs (binary; prescribed NSAIDs or not prescribed NSAID), previous elbow fractures (binary; previous elbow fracture or no previous elbow fracture), diabetes status (binary; diabetic or non-diabetic), smoking status (binary; current regular smoker or not a current regular smoker), drinks alcohol (binary; drinks alcohol or does not drink alcohol), randomised treatment group, time, and treatment group-by-time interaction as fixed effects and including treating centre and participant as random effects.

The DASH measure will be taken twice at baseline; pre and post-injury. We have outlined that the preinjury measure will be used in the primary analysis model as pre-injury function is more relevant. The post-injury scores will be examined for balance and if there is an imbalance across arms this will also be added to our primary analysis model.

The correlation of observations within participants over time will be modelled using participant as a random effect. The Akaike information criterion (AIC) will be used to compare models specifying different correlation structures (smaller values preferred), the most appropriate pattern will be used for the final model. All model assumptions will be checked, and if they are in doubt transformations of the outcome data will be considered. The estimated treatment group differences at 4 months will be reported as the primary endpoint with its associated one-sided 97.5% confidence interval. Example tables are provided in the appendix (Section 15.2.2).

Non-inferiority will be accepted if the upper bound of the one-sided 97.5% confidence interval (equivalent to the upper two-sided 95% confidence limit) for the treatment difference at 4 months lies below the non-inferiority margin of 10 points. Further details on this decision can be found in appendix 15.1.

Primary analysis will be checked by a second statistician on completion, this will be documented using *F16: Primary Analysis Sign Off* Form.

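### The CACE compliance variable is not fixed: read literally it does not contrast suture with wire, and the model described cannot be fitted with the command named

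*SAP*

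**What the plan says.** SAP section 11.6, under Intervention adherence, plans a CACE analysis that "will be undertaken for the primary outcome (DASH score at 4-months"). It specifies four things.

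- **Variable.** "Compliance will be based on whether the participant received allocated treatment", supplemented by surgeon self-report and "image analysis of intra-operative images for fidelity".
- **Substitution.** "The primary analysis model will be repeated but the variable for randomised treatment group will be replaced with the variable for compliance".
- **Method.** "A two-stage IV regression approach will be used with mixed-effects regression to reflect the primary analysis".
- **Software.** "This model will be fit using the ivregress stata command", and "The option vce (cluster) will be used to account for repeated measures".

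The primary model to be repeated (section 11.5) uses the DASH at 4, 12 and 18 months and has "treatment group-by-time interaction as fixed effects and including treating centre and participant as random effects". Appendix 15.1 codes randomised arm as 1 for suture and 0 for wire. Appendix 15.2.2 says the sensitivity analysis will be laid out like Table 3, that is, as an adjusted suture-versus-wire mean difference with a one-sided 97.5% interval.

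The SAP does not say how compliance is scored in the wire arm, whether fidelity applies to one arm or both, what the instrument is, how the interaction is instrumented, or how centre enters the model.

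**The concern.** Both arms are active operations (section 3), so each has an allocated treatment that a participant can receive or not. An indicator of having received the allocated operation is 1 for a wire participant who got wire and 1 for a suture participant who got suture. Put in place of arm, it contrasts compliers with non-compliers. If arm is used as the instrument, the denominator of the IV estimate is the difference in compliance rates between arms, which may be small, zero or negative. The result would then appear in a table whose layout presents it as suture minus wire.

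The stakes come from the design. The primary analysis is by intention to treat (section 11.2), and no per-protocol analysis of the DASH is planned. If suture is truly worse, crossover pulls the ITT difference towards zero, which favours a non-inferiority claim. Sections 11.8 and 11.9 allow for the possibility of many crossovers. CACE is the only planned check of the primary result against non-adherence.

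A second problem is separate. The paragraph names a mixed-effects model and a command that has no random effects.

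**Working it through.** **Inputs from the SAP.** Margin 10, SD 23, 224 analysed and 280 in total (section 8); 1:1 allocation (section 9). The CACE paragraph gives no figures, so the compliance rates and effects below are assumptions.

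**The plan's own figure.** n per arm = 2 × 23² × (1.960 + 1.282)² / 10² ≈ 111.2, rounded up to 112. That gives 224 in total, and 224 / 0.80 = 280. Both match the SAP. The simulation below uses 224 and SD 23.

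**Formulas.** Let Z be randomised arm (1 = suture), p1 the proportion of the suture arm receiving suture, and p0 the proportion of the wire arm receiving wire. Non-compliers are assumed to receive the other operation. With Z as instrument, the IV estimate is ITT / (E[X|Z=1] − E[X|Z=0]).

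- X = C, received the allocated operation: denominator p1 − p0.
- X = D, received suture: denominator p1 − (1 − p0) = p1 + p0 − 1.
- X = Z×C, received suture as allocated and 0 throughout the wire arm: denominator p1.

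**Assumed ITT difference of +2.**

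| p1 / p0 | C | D |
|---|---|---|
| 90% / 95% | 2 / −0.05 = −40 | 2 / 0.85 = +2.35 |
| 85% / 97% | 2 / −0.12 = −16.7 | 2 / 0.82 = +2.44 |
| 95% / 93% | 2 / 0.02 = +100 | 2 / 0.88 = +2.27 |

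**Assumed true effect of receiving suture of +5**, so ITT = 5 × (p1 + p0 − 1).

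| p1 / p0 | ITT | C | D | Z×C |
|---|---|---|---|---|
| 90% / 98% | 4.4 | −55 | 5.0 | 4.89 |
| 95% / 95% | 4.5 | undefined | 5.0 | 4.74 |
| 98% / 90% | 4.4 | +55 | 5.0 | 4.49 |
| 80% / 98% | 3.9 | −21.7 | 5.0 | 4.88 |
| 90% / 100% | 4.5 | −45 | 5.0 | 5.00 |

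**Simulation** (224 participants, SD 23, 4000 runs, true effect +5). The central 95% of estimates were:

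- At 90% / 98%: C −258 to 23.5, D −1.9 to 11.8, ITT −1.6 to 10.4.
- At 95% / 95%: C −797 to 809, with the denominator exactly zero in 11.6% of runs.

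If C simply replaces arm with no instrument, the median estimate lies between −1.4 and +2.3 across these scenarios, instead of +5.

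**Model and command, side by side.**

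- The primary model has random effects for centre and participant. ivregress is a single-equation linear IV command with no random effects. Clustered errors are offered in place of the participant effect; nothing is offered for centre.
- Repeating the primary model brings in compliance and compliance-by-time, both endogenous. No instruments are stated for either.
- The target is 4 months only, yet the error structure is chosen for repeated measures.
- In the missing-data part of the same section, the SAP recognises that rctmiss takes fixed effects only and rewrites the model to suit. It does not do so for ivregress.

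**The case against.** A reader might infer that the SAP has committed itself to an analysis that cannot estimate suture versus wire. The text does not go that far. Compliance is said to be based on receipt and fidelity, and no 0/1 rule is given. The sub-heading concerns adherence to the intervention, suture is the arm labelled intervention, and sections 3 and 10 speak of fidelity to the suture technique. A statistician could therefore code suture received as allocated, with 0 throughout the wire arm. With arm as instrument that is usable: 4.5 to 5.0 against a true 5 above, and exact when nobody crosses from wire to suture. This stands. The defect is an undefined variable whose literal reading fails, not a proven wrong estimand.

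A reader might also infer that the choice of command alone spoils the contrast. It does not. Linear two-stage least squares on the operation received, with clustered errors, still estimates suture versus wire. The mismatch affects standard errors, the handling of centre and comparability with the primary model.

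It can be added that arm is the conventional instrument in a randomised trial, with arm-by-time following for the interaction. That makes the silence less serious, but a pre-specified analysis should still say so.

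Finally, this is a sensitivity analysis, and the large figures rest on assumed compliance rates. Both points are correct. On the same assumptions, a well-defined CACE moves +2 only to between +2.27 and +2.44, far from the margin of 10.

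**Conclusion.** The point holds as one of definition and internal consistency. Section 11.6 leaves the compliance variable and its instrument open. If its words are followed literally, the estimate is unstable and can take the wrong sign: an assumed ITT difference of +2 becomes −40, −16.7 or +100 depending on which arm complies less and by how much. The same data give +2.27 to +2.44 for suture received. These sizes apply only to the literal coding, with arm as instrument and the assumed compliance rates; the SAP supplies none. If fidelity were judged only or mainly in the suture arm, suture compliance would tend to be lower and the denominator negative, so that a true harm could appear as a benefit.

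The conflict between mixed-effects regression and ivregress is present under any coding, as are the missing treatment of centre and the unstated instruments for the by-time terms. The primary ITT analysis, the decision rule and the sample size are unaffected. The matter deserves correction because this is the only adherence-based check on an ITT non-inferiority conclusion.

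**What to change.** - **Variable.** Define the endogenous variable as the operation actually received, 1 = tension suture repair and 0 = tension band wiring, coded the same way in both arms. State how anyone who received neither is handled.
- **Instrument and model.** Name randomised arm as the instrument. Fit ivregress 2sls to the 4-month DASH with the primary model's covariates, centre as fixed effects and robust standard errors. Alternatively, keep all time points, instrument receipt and receipt-by-time with arm and arm-by-time, cluster by participant, and report the 4-month contrast.
- **Wording.** Delete the reference to mixed-effects regression from the CACE paragraph.
- **Fidelity.** Handle technique fidelity in a separate analysis with an explicit rule for each arm. Do not score low-fidelity suture operations as 0 alongside wire. Those participants still received sutures, so allocation could affect their DASH without changing the variable, which breaks the exclusion restriction. If that coding is kept, state the assumption it needs.
- **Reporting.** Give the 4-month upper one-sided 97.5% limit and compare it with the margin of 10.

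The cost is SAP wording and code; no new data are needed. Centre moves from random to fixed effects. The interval is somewhat wider than under ITT: in the 90% / 98% simulation the range is 13.7 points wide (−1.9 to 11.8) against 12.0 (−1.6 to 10.4). The 4-month-only version also loses participants who have later DASH scores but none at 4 months, whom the primary model would keep.

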7.4 Management database

All participant-reported data is identified solely by the unique participant trial ID. No other identifying details will be printed or input onto these documents. These CRFs are returned by post or electronically to YTU where they are scanned, using Teleform data capture software, into a bespoke data management system. This system is separate from the trial management system and contains no identifying details. All data are error checked and validated to ensure accuracy according to procedures detailed in the trial Data Management Plan. The paper CRFs are held securely in a controlled access area in locked cabinets but separate from the consent forms.

Both the trial management system and the data management systems are held on secure University of York servers with access limited to specified members of YTU staff as detailed in the delegation log.

8. Sample Size

There will be a 24-month recruitment period for the SOFFT trial. The total target sample size will be 280 participants. This was calculated using the standard deviation values for the DASH which range from 16 to 28 depending on the population under study [2, 8-12]. To be conservative a SD of 23 was assumed. Minimal clinical important differences for the DASH are around 10 points from individual studies using anchor-based methods [3, 10]. We estimate that a 10 point difference on the DASH at 4 months represents the threshold at which differences become important, and which would represent an appropriate non-inferiority margin. For 90% statistical power, 224 participants are required to establish non-inferiority of suture fixation compared with tension band wiring technique within a margin of 10 points on the DASH (SD=23), based on the upper limit of a 95% two-sided confidence interval (equivalent to a one-sided 97.5% confidence interval). Assuming 20% attrition at 4 months follow-up, gives the total target sample size 280.

9. Randomisation and blinding

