Randomisation will be undertaken by York Trials Unit (YTU). When patients have given written informed consent and all the baseline forms have been completed, the authorised site research staff will contact YTU either by accessing a secure, internet-based randomisation service website hosted by York Trials Unit (https://ytu.york.ac.uk/YorkRand/) to obtain the patient's treatment allocation and enrol the patient into the study. Research staff will be required to provide the patient's trial identification number and other details to confirm patient eligibility in order to avoid inappropriate entry of patients into the trial. Participants will be randomly allocated in a 1:1 ratio to either tension suture repair or tension band wiring, using computer generated permuted blocks of random sizes, stratified by centre.

The Statistician will not be blinded to group allocation, nor will other members of the study team who are actively involved in the administration of the study. Participants will not be informed of which treatment they have received and the surgical wound is the same. However, if the wire protrudes or becomes uncomfortable, or the participant has sight of the x-ray, it may become apparent to the participant which intervention they have received. The investigator will record on the 4-month follow-up CRF whether they are aware of any inadvertent un-blinding of the participant (without asking the participant).

10. Analysis of internal pilot phase

There will be a 9-month internal pilot phase to assess assumptions about recruitment and the fidelity of implementing the tension suture repair technique.

The recruitment rate (defined as the proportion of eligible patients recruited) and 95% confidence interval (CI) will be estimated from the data collected up to the end of the pilot phase.

A CONSORT diagram will be produced to show the flow of participants through the study and the following outcomes calculated: number of eligible patients; proportion of eligible patients approached for consent; proportion of eligible patients not approached and reasons why; proportion of patients approached who provide consent; proportion of patients approached who do not provide consent; proportion of patients providing consent who are randomised; proportion of patients randomised who do not receive the randomly allocated treatment; proportion of patients dropping out between randomisation and follow-up.

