11.2 Analysis principles and populations

Analyses will follow the principles of intention-to-treat (ITT) with participant's outcomes analysed according to their original, randomised group, where data are available, irrespective of deviations based on non-compliance. One-sided 97.5% confidence limits (equivalent to the upper bound of the two-sided 95% confidence interval) will be reported for the primary outcome and secondary analysis of DASH scores. There will be no pre-defined non-inferiority margins for the remaining secondary outcomes, these will be compared for evidence of superiority and two-sided tests at the 5% significance level will be used.

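### The primary model drops any participant with one missing baseline covariate: an avoidable, probably small loss that an arm-blind imputation rule would remove

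*SAP*

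**What the plan says.** Section 11.5 fits a mixed-effects model to DASH at 4, 12 and 18 months. It adjusts for seven baseline covariates: pre-injury DASH, age, prescribed NSAIDs, previous elbow fracture, diabetes, smoking and alcohol. Post-injury DASH becomes an eighth if the arms are found to be imbalanced on it.

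Under missing data, section 11.6 presents this model as a way of limiting the loss, because it "allows the inclusion of any patient with complete baseline data and valid outcome data at one or more follow-up points". No section says what happens when a baseline covariate is missing. The scoring rules under section 6.2 give no DASH score when fewer than 27 of the 30 items are answered.

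Section 11.2 states the intention-to-treat principle as "participant's outcomes analysed according to their original, randomised group, where data are available".

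Section 11.6 also plans a logistic regression to "predict non-response (no questionnaires received post-randomisation") and then repeats the primary analysis with the significant predictors as added covariates.

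On size, section 8 says: "For 90% statistical power, 224 participants are required to establish non-inferiority of suture fixation", "within a margin of 10 points on the DASH (SD=23"), and then "Assuming 20% attrition at 4 months follow-up, gives the total target sample size 280".

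**The concern.** The inclusion rule has two conditions. The outcome condition is generous: one valid DASH at any of three times is enough. The covariate condition is strict: all seven values must be present. A participant who attends at 4 months and completes the DASH in full still leaves the primary analysis if the pre-injury DASH has only 26 items or one yes/no field is blank. The primary endpoint was observed and is discarded.

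The re-run with predictors of non-response adds covariates. If the same rule applies there, the check on missing-data bias can lose further participants, and its result then differs from the primary one partly because the analysed set has changed.

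What is at stake is some precision and the completeness of the randomised set. With no rule in place, a missing covariate leads either to exclusion or to an unplanned choice, and section 9 says the statistician is not blinded to allocation.

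**Working it through.** **Inputs from the SAP.** Margin 10, SD 23, 90% power and 20% attrition at 4 months (section 8). One-sided 0.025, from "based on the upper limit of a 95% two-sided confidence interval (equivalent to a one-sided 97.5% confidence interval"). Allocation 1:1 (section 9).

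**Assumptions.** A true difference of zero, which the SAP does not state but which reproduces its figure. The share m of otherwise analysable participants with at least one missing covariate, for which the SAP gives no rate. Independence of m from attrition. No gain in precision from covariates or repeated measures. Complete baseline data is read as complete model covariates; read as all baseline data, the rule would exclude more.

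**Step 1: the plan's own figure.**

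n per arm = 2 × 23² × (1.960 + 1.282)² / 10² = 1058 × 10.51 / 100 = 111.2, rounded up to 112. Total 224. Then 224 / (1 − 0.20) = 280. Both stated figures are reproduced.

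**Step 2: power after covariate loss.**

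N = 280 × 0.80 × (1 − m), and power = Φ(10 / (23 × √(4/N)) − 1.960).

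For m = 0: 23 × √(4/224) = 3.073; 10 / 3.073 = 3.254; 3.254 − 1.960 = 1.294; power 90.2%.

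| Assumed overall loss m | N analysed | Power |
|---|---|---|
| 0 | 224.0 | 90.2% |
| 1% | 221.8 | 89.9% |
| 2% | 219.5 | 89.6% |
| 5% | 212.8 | 88.7% |
| 10% | 201.6 | 87.0% |

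**Step 3: how seven covariates could add up.** If each were missing independently in a share q of participants, m = 1 − (1 − q)⁷.

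| q per covariate | m | N analysed | Power |
|---|---|---|---|
| 0.5% | 3.4% | 216.3 | 89.2% |
| 1% | 6.8% | 208.8 | 88.1% |
| 2% | 13.2% | 194.5 | 85.8% |

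Independence makes these high values for a given q. If blanks cluster in the same participants, m is smaller.

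**Step 4: with the rule replaced.** If missing covariates are imputed, m returns to 0, N to 224 and power to 90.2%.

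**Step 5: the non-response model.** At the planned attrition, 0.20 × 280 = 56 participants have no 4-month DASH. The logistic model counts as events only those who return nothing at all. If that is 25%, 50% or 75% of the 56 (assumed), it has 14, 28 or 42 events. The two definitions can therefore differ, but this does not show that the planned one is wrong.

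**The case against.** **Covariate loss will be slight.** Section 9 has randomisation follow completion of all baseline forms. The template tables in 15.2.1 give a missing row for sex and ethnicity but none for smoking, alcohol, diabetes or previous elbow fracture. That is weak evidence, but it points the same way. The power figures also ignore covariate adjustment: a 5% loss is offset if the covariates explain 5% of outcome variance (multiple correlation √0.05 ≈ 0.22, itself an assumption). This stands and keeps the point modest. It does not justify the rule, since imputing would keep the same gain from adjustment and the participants as well.

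**A reader might infer that the rule contradicts intention-to-treat.** The SAP does not support that. Section 11.2 defines the principle as analysis by randomised group and limits it to available data, and section 11.6 discloses the restriction. This is an available-data analysis with an unnecessarily narrow set.

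**A reader might infer bias.** The covariates are taken to be recorded before randomisation, so exclusion for a missing one should not depend on arm. No arm-related bias is expected from this alone.

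**A reader might infer that the non-response definition is an error, because the endpoint is the 4-month DASH.** Apart from covariate exclusions and unscorable forms, participants who return nothing are the ones the repeated-measures model loses. Someone who misses only month 4 still contributes through later scores under missing at random. Section 11.6 also describes an optional pattern-mixture analysis of the 4-month outcome, reports missing data by arm and summarises missingness patterns. The definition is defensible.

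**Conclusion.** The point holds as one of efficiency and completeness. As written, the primary model excludes randomised participants with an observed follow-up DASH because of one missing covariate, although a nearly free alternative would keep them. The section 8 calculation is correct, but it makes no allowance for this loss.

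The cost is about 0.3 percentage points of power at an assumed 1% overall loss, 1.5 at 5% and 3.2 at 10%. With baseline forms completed before randomisation, the low end is more likely. These figures rest on an assumed loss rate, a true difference of zero and an unadjusted calculation. The SAP does not support a charge of bias between arms, of a breach of its own analysis principle, or of a wrongly defined non-response model.

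**What to change.** In section 11.6, replace the complete-baseline requirement with a rule fixed in advance: missing baseline covariates are imputed without reference to treatment arm. For example, use the overall mean for pre-injury DASH (and for post-injury DASH if it enters the model), and the mode or a missing-indicator category for the yes/no items. State that everyone with at least one valid follow-up DASH is analysed, and apply the same rule to the re-run that adds predictors of non-response. Report how many values were imputed, by covariate and arm.

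The cost is a few sentences of SAP text, an entry in the amendment log and a few lines of code. The downside is a minor approximation in a few covariate values. Because the values precede randomisation and are filled in blind to arm, this does not bias the treatment comparison.

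Optionally, repeat the non-response logistic model with no valid 4-month DASH as its outcome. This would add to the planned model, not replace it.
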